10.5 Derived and transformed data

Immunogenicity

For a given subject cohort and the analysis of a given measurement, missing or unevaluable measurements will not be replaced. Therefore an analysis will exclude subjects with missing or unevaluable measurements.

- The cut-off value is defined by the laboratory before the analysis and is described in Section 5.5.2.
- A seronegative subject is a subject whose titer or concentration is below the cut-off value.
- A seropositive subject is a subject whose titer or concentration is greater than or equal to the cut-off value.
- Antibody concentrations or titers below the cut-off of the assay will be given an arbitrary value of half the cut-off for the purpose of GMC or GMT calculation.

Other

Subjects who missed reporting symptoms (solicited or unsolicited or concomitant medications) will be treated as subjects without symptoms (solicited or unsolicited or concomitant medications, respectively).

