10.4 Study cohorts to be evaluated

A total of 6 cohorts are defined for the purpose of analysis.

- Three cohorts that will be used for the analysis of the primary vaccination course:
 - the Total vaccinated cohort
 - the ATP cohort for safety
 - the ATP cohort for immunogenicity (used for the analysis of the co-primary objectives of immunogenicity)
- Three cohorts that will be used for the analysis of the booster phase:
 - the Total vaccinated cohort

- the ATP cohort for safety
- the ATP cohort for immune memory

The Total vaccinated cohort (Primary vaccination)

The Total vaccinated cohort will include all subjects vaccinated in the primary phase of the study. For the Total analysis of safety, this will include all subjects vaccinated in the primary phase of the study with at least one vaccine administration documented in the primary phase. For the Total analysis of immunogenicity / efficacy, this will include subjects vaccinated in the primary phase of the study for whom data concerning immunogenicity/efficacy endpoint measures are available. The Total vaccinated cohort analysis will be performed per treatment actually administered.

According to protocol (ATP) cohort for safety (Primary vaccination)

The According to protocol (ATP) cohort for safety will include all subjects:

- who have received at least one dose of study vaccine/control according to their random assignment,
 - with sufficient data to perform an analysis of safety,
 - for whom the administration route of study vaccine/control is known and correct,
 - who have not received a vaccine not specified or forbidden in the protocol,
 - who did not receive a replacement vaccine,
- during the primary vaccination course.

According to protocol (ATP) cohort for immunogenicity (Primary vaccination)

The According to protocol (ATP) cohort for immunogenicity will include all evaluable subjects (i.e. those meeting all eligibility criteria, complying with the procedures defined in the protocol, and with no elimination criteria during the study) from the ATP cohort for safety for whom assay results are available for antibodies against at least one study vaccine antigen component at Visit 4.

The Total vaccinated cohort (Booster vaccination)

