10.6.3 Analysis of Safety

The primary analysis will be based on the Total vaccinated cohort. If the percentage of enrolled subjects excluded from the ATP cohort for safety is more than 5%, a second analysis based on this ATP cohort will be performed to complement the Total vaccinated cohort analysis.

The percentage of subjects with at least one local adverse event (solicited and unsolicited), with at least one general adverse event (solicited and unsolicited) and with any adverse event during the 4-day solicited follow-up period will be tabulated with exact

95% CI after each vaccine dose and overall. The percentage of doses followed by at least one local adverse event (solicited and unsolicited), by at least one general adverse event (solicited and unsolicited) and by any adverse event will be tabulated, overall vaccination course, with exact 95% CI.

The percentage of subjects reporting each individual solicited local and general adverse event during the 4-day solicited follow-up period will be tabulated with exact 95% CI. The percentage of doses followed by each individual solicited local and general adverse event will be tabulated, overall vaccination course, with exact 95% CI.

The same tabulation will be performed for grade 3 adverse events and for adverse events with relationship to vaccination.

The proportion of subjects with at least one report of unsolicited adverse event classified by the Medical Dictionary for Regulatory Activities (MedDRA), and reported up to 30 days after vaccination will be tabulated with exact 95% CI. The same tabulation will be performed for grade 3 unsolicited adverse events and for unsolicited adverse events with a relationship to vaccination.

Serious adverse events and withdrawal due to adverse event(s) will be described in detail.

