10.7.2 Analysis of safety

All analyses will be based on the Total vaccinated cohort. If the percentage of enrolled subjects excluded from the ATP cohort for safety is more than 5%, a second analysis based on this ATP cohort will be performed to complement the Total vaccinated cohort analysis.

The percentage of subjects with at least one local adverse event (solicited and unsolicited), with at least one general adverse event (solicited and unsolicited) and with any adverse event during the 4-day solicited follow-up period will be tabulated with exact 95% CI after each vaccine dose and overall.

The percentage of subjects reporting each individual solicited local and general adverse event during the 4-day solicited follow-up period will be tabulated with exact 95% CI.

The same tabulation will be performed for grade 3 adverse events and for adverse events with relationship to vaccination.

The proportion of subjects with at least one report of unsolicited adverse event classified by the Medical Dictionary for Regulatory Activities (MedDRA), and reported up to 30 days after vaccination will be tabulated with exact 95% CI. The same tabulation will be performed for grade 3 unsolicited adverse events and for unsolicited adverse events with a relationship to vaccination.

Serious adverse events and withdrawal due to adverse event(s) will be described in detail.

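### Counting infants without a solicited-symptom record as symptom-free can only lower the solicited reactogenicity rates wherever records are missing

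*Protocol*

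**What the plan says.** Section 10.5 (Derived and transformed data) holds two opposite missing-data rules. For immunogenicity, "missing or unevaluable measurements will not be replaced", and the subject leaves that analysis. For safety, "Subjects who missed reporting symptoms (solicited or unsolicited or concomitant medications) will be treated as subjects without symptoms".

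Section 10.6.3 says of the primary course: "The primary analysis will be based on the Total vaccinated cohort". Section 10.7.2 says of the booster: "All analyses will be based on the Total vaccinated cohort". Under section 10.4 the primary-course cohort for safety is "all subjects vaccinated in the primary phase of the study with at least one vaccine administration documented in the primary phase", and the booster cohort is defined in the same way. Neither definition asks for symptom data.

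The estimates affected include "The percentage of subjects reporting each individual solicited local and general adverse event during the 4-day solicited follow-up period", given with exact 95% confidence intervals, and the corresponding per-dose percentages over the primary course.

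The ATP cohort for safety does ask for subjects "with sufficient data to perform an analysis of safety". The condition for analysing it begins "If the percentage of enrolled subjects excluded from the ATP cohort for safety is more than 5" per cent. It then complements the Total vaccinated analysis and does not replace it.

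**The concern.** Solicited symptoms are actively recorded by field workers at home on days 0 to 3 (Table 5-1, section 5.4). Absence is itself a recorded value: Table 8-3 has a grade 0 for pain, irritability, drowsiness and appetite, and temperature is written down whatever it is. A blank record is therefore not a record of absence. Section 10.5 turns it into one and so assigns the most favourable outcome to every unobserved infant.

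Reactogenicity after each dose, in both groups, is a stated secondary objective (section 2.2) for a new infant combination. An error that can only make the vaccine look better tolerated runs in the wrong direction. If follow-up differs between groups, the tables could also show a difference that is not there, or hide one that is.

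**Working it through.** The protocol gives no expected reactogenicity rate and no expected share of missing records, so there is no stated figure to reproduce. The rates and missing shares below are assumptions; the group size of 140 (280 in total) is from sections 3 and 4.1.

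**Direction.** Let m be the share without a record, p the rate among infants with a record and q the rate among those without.
- True rate: (1 − m)p + mq
- Tabulated rate under 10.5: (1 − m)p
- Bias: −mq, which is never above zero. It is zero if m = 0 or q = 0.

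**Size, missing at random (q = p).** The tabulated rate is p(1 − m).

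| True rate | 5% missing | 10% missing | 20% missing |
|---|---|---|---|
| 10% | 9.5% | 9.0% | 8.0% |
| 40% | 38.0% | 36.0% | 32.0% |
| 50% | 47.5% | 45.0% | 40.0% |
| 80% | 76.0% | 72.0% | 64.0% |

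**One worked group.** Take 140 vaccinated, 14 without a record and 63 with the symptom. Under 10.5: 63/140 = 45.0% (exact 95% CI 36.6 to 53.6). With documented records as denominator: 63/126 = 50.0% (41.0 to 59.0).

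**Coverage of the exact 95% CI at N = 140, true rate 50%:** 96.6% with none missing, 93.3% with 5%, 82.4% with 10% and 39.6% with 20%. For an uncommon symptom (true rate 10%) with 10% missing, coverage is still 96.6%.

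**Between groups.** True rate 40% in both groups, 5% missing in one and 15% in the other: 0.40 × 0.95 = 38% against 0.40 × 0.85 = 34%, a spurious difference of 4 points.

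**Does the ATP safety analysis catch this?**
- The condition is more than 5% of enrolled subjects excluded, and 5% of 280 is 14. Exactly 14 exclusions do not meet it. Unlike the immunogenicity conditions in sections 10.6.2 and 10.7.1, the safety condition is not worded per vaccine group. Read as pooled, 14 infants without data could all sit in one group (14/140 = 10%), giving a spurious difference of 0.10 × 50 = 5 points at a true rate of 50%, with no second analysis required.
- The data criterion is set per subject. Each group has 140 × 3 = 420 primary doses. If 42 were undocumented (10%), each in a different infant, every infant would still have data for two doses and could remain in the ATP cohort. If the 10.5 rule is applied dose by dose, a per-dose rate of 40% becomes 0.40 × 378/420 = 36% in both cohorts.

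**The case against.** The strongest reply is that little may be missing. Collection does not rely on parents returning cards: field workers visit daily, and the investigator checks and transcribes the diaries at the next visit. With nothing missing the bias is zero, and nothing in the protocol points to 10% or 20%. A reader might infer that every solicited rate in this trial is biased; the documents do not support that. What stands is that the rule has no effect only when records are complete or the unobserved infants were symptom-free.

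Second, larger gaps would trigger the ATP analysis. If 5% and 15% of the two groups were excluded for lack of data, that is 7 + 21 = 28 of 280, or 10%, well over the threshold. This is a real safeguard, but it misses the cases shown above and leaves the main tables unchanged.

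Third, a reader might infer that the confidence intervals are always too narrow. They are not. At 63 symptomatic infants the rule narrows the interval (width 17.0 against 18.1 points), but at 101 it widens it: 101/126 gives 72.1 to 86.7 (width 14.6), while 101/140 gives 63.9 to 79.4 (width 15.4). The general fault is location, not width.

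Fourth, a reader might infer that serious harm is hidden. Deaths and hospitalisations are serious adverse events, reported within 24 hours and described in detail whatever section 10.5 says, and vaccine-related grade 3 systemic events go to the Local Safety Monitor and the data monitoring committee. The rule affects tabulated percentages, not these routes.

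Finally, section 10.5 speaks of subjects, so applying it to single doses is a plausible reading and not an explicit statement.

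**Conclusion.** The rule is wrong as written for solicited symptoms and should be corrected. Where diary data are missing, the tabulated solicited rates can only be biased downwards, by the missing share times the symptom rate among the infants not observed: 4 points at a true rate of 40% with 10% missing at random, 2 points with 5%. Unequal missingness can create or mask a group difference of similar size. The ATP safety analysis is a partial safeguard only.

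The sizes rest on assumed rates and missing shares; the direction does not. Reactogenicity here is secondary and tabulated without a test or margin, so no co-primary conclusion and no sample size figure changes. That is why this is a correction worth making rather than a bar to the trial.

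**What to change.** In section 10.5, separate solicited symptoms from the rest of the rule:
- For solicited symptoms, the denominator is the subjects (per-subject tables) or doses (per-dose tables) with documented solicited-symptom data, in every safety cohort and in both phases.
- Show the number of subjects and doses without such data, by group and dose.
- Keep the convention that no report means no event for unsolicited adverse events only.
- Optionally, add an extreme-case table that counts undocumented doses as symptomatic, to bound the effect.

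The documented denominator recovers the true rate only if missingness is unrelated to symptoms, so the missing counts must stand beside the rates. The cost is a wording change and a slightly smaller N in the reactogenicity tables; no new data, visits or subjects are needed.

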10.6 Final analyses for the primary vaccination course

10.6.1 Analysis of demographics/baseline characteristics

Demographic characteristics (age in weeks, gender, race) of each study cohort will be tabulated.

The mean age (plus range and standard deviation) by gender of the enrolled subjects, as a whole, and per group, will be calculated.

The distribution of subjects enrolled among the study sites will be tabulated as a whole and per group.

10.6.2 Analysis of Immunogenicity

The analysis of immunogenicity will be based on the ATP cohort for immunogenicity. If, for any vaccine group, the percentage of enrolled subjects with serological results excluded from this ATP cohort is more than 5%, a second analysis based on the Total vaccinated cohort will be performed to complement the ATP analysis.

Analysis of immunogenicity will be as follows:

Descriptive analysis

For each treatment group, one month after the third dose of the primary vaccination course, and in the mother prior to her child's vaccination, for each serological assay done:

- Geometric Mean antibody Concentrations/Titers (GMCs/GMTs) with 95% confidence intervals (CIs) will be tabulated for each antibody. Calculation of the GMCs/GMTs is performed by taking the anti-log of the mean of the log concentration/titer transformations.
- Seropositivity / seroprotection rates with exact 95% CIs will be calculated.

- Antibody concentrations/titers post-vaccination will also be investigated using reverse cumulative curves for each antigen and serogroup.

Inferential analysis

The inferential analysis will be done sequentially.

1. If the lower limit of the 95% CI for the percentage of subjects with SBA-MenC is above 80%, one will conclude that Tritanrix™-HepB/Hib-MenAC is immunogenic for MenC.
2. If, in addition, the lower limit of the 95% CI of subjects with SBA-MenA is above 80%, one will conclude that Tritanrix™-HepB/Hib-MenAC is immunogenic for MenA.
3. If, in addition, the upper limit of the 95% CI for the group difference for anti-PRP is below 10% one will conclude non-inferiority with respect to anti-PRP.
4. If, in addition, the upper limit of the 95% CI for the group difference for anti-Tetanus is below 10% one will conclude non-inferiority with respect to anti-Tetanus.
5. If, in addition, the upper limit of the 95% CI for the group difference for anti-Diphtheria is below 10% one will conclude non-inferiority with respect to anti-Diphtheria.
6. If, in addition, the upper limit of the 95% CI for the anti-BP GMC ratio (control vaccine / new vaccine) is below 1.5 one will conclude non-inferiority with respect to anti-BP.
7. If, in addition, the upper limit of the 95% CI for the group difference for anti-HBs is below 10% one will conclude non-inferiority with respect to anti-HBs.

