- At 12 months of age, to assess the reactogenicity and safety of the 10 µg meningococcal A and C polysaccharides when given to subjects primed with either Tritanrix™-HepB/Hib-MenAC or with Tritanrix™-HepB/ Hiberix™.

Study design

- Experimental design: 2 parallel groups of 140 subjects each to receive either of the following vaccines:
 - Tritanrix™-HepB/Hib-MenAC
 - Tritanrix™-HepB/Hiberix™
- Active control group (Tritanrix™-HepB/Hiberix™)
- Indication: primary vaccination of infants according to the Expanded Program of Immunization (EPI) schedule (6, 10, 14 weeks of age).
- BCG and OPV vaccines can be given at birth or up to at least 2 weeks before study start. OPV can then be given concomitantly with the study vaccines at 6, 10 and 14 weeks of age or at any time during the study, whichever is more appropriate. At 9 months of age, all subjects will receive measles and yellow fever vaccines.
- At 12 months of age, all subjects will be evaluated for antibody persistence and will be administered 10 µg of each plain meningococcal serogroup A and C polysaccharides (one fifth of a dose of Mencevax™ AC) to evaluate the immune memory induced by vaccination.
- After study end, one dose of Mencevax™ ACWY will be offered to the Tritanrix™-HepB/Hiberix™ control group to protect them against meningococcal diseases of these serogroups: Mencevax™ ACWY will be given when the child is two years of age, or, if a meningitis epidemic occurs, earlier in the second year of life.

- Treatment allocation: randomized (1:1)
- Blinding: Double-blind
- Study duration per subject: approximately **22.5 months to include the retrospective follow-up of SAE(s) up to the time that subjects are at least 24 months of age.**
- Data collection: Hard copy Case Report Form (CRF)
- For all subjects: 4 blood samples (3.5 ml):
 - immediately before the first dose of the primary vaccination course
 - one month after the third dose of the primary vaccination course
 - just prior to administration of the plain polysaccharides of serogroups A and C
 - one month after the administration of the plain polysaccharides of serogroups A and C.
- 4-day follow-up of solicited local and general symptoms after each dose.
- One month follow-up for unsolicited symptoms after each dose.
- Reporting of serious adverse events during the entire study period.

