5.5.3 Serology plan

Pre-vaccination (Day 0) serum samples will be tested in all subjects for antibodies against SBA-MenA, SBA-MenC, anti-PSA, anti-PSC, diphtheria toxoid, pertussis antigen and recombinant DNA hepatitis B surface antigen (no pre-vaccination testing of anti-TT and anti-PRP is foreseen as immunogenicity results of the previous clinical study were highest for these two antibodies).

Post-vaccination III and pre-booster serum samples will be tested in all subjects for antibodies against all vaccine antigens (SBA-MenA, SBA-MenC, anti-PRP, anti-PSA, anti-PSC, diphtheria and tetanus toxoids, pertussis antigen and recombinant DNA hepatitis B surface antigen).

The post-booster serum sample taken from all children will be tested for SBA-MenA and SBA MenC, anti-PSA and anti-PSC antibodies.

In case of insufficient blood sample volume to perform assays for all antibodies, they will be analyzed according to the following priority ranking:

- SBA-MenA
- SBA-MenC
- anti-PRP (only for Post vacc III and pre-booster)
- anti-diphtheria (Vero-cell assay only when required for Post vacc III and Pre-booster)
- anti-HBs
- anti-tetanus, (only for Post vacc III and pre-booster)
- anti-BP
- anti-PSA
- anti-PSC

Any additional serology on antigens contained in the study vaccines may be performed if deemed necessary by GlaxoSmithKline Biologicals, or if any findings in the present study or in other studies necessitate investigation of the immunogenicity of the vaccine. In this case, the ranking above may also be changed.

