The immunogenicity analysis of the dose-range study has highlighted the importance of having an accurate picture of the pre-vaccination maternal antibody levels in the infants (especially hepatitis B, diphtheria, pertussis and meningococcal serogroup A and C antibodies) as it appears that the response to the vaccine (especially to the hepatitis B, diphtheria, pertussis and meningococcal serogroups A and C antigens) can be affected by these levels. It has therefore been decided to add an additional blood sampling from the infants in this study at the

pre-vaccination timepoint and to drop the planned blood sampling from the mother. The protocol has been amended accordingly, including changes to the objectives and endpoints where relevant. Furthermore since the mother is no longer required to accompany the child for the first visit, the protocol (and the informed consent) has been changed to allow another parent or guardian to provide informed consent.

As it is possible that the collection of the additional blood sample from the infants in the study may lead to an increased rate of withdrawal/drop-out of subjects from the study, the sample size has been increased from 260(130/group) to 280 (140/group) to ensure that the required number of evaluable subjects is reached.

As the committee that will be set up to oversee the ethical and safety aspects of the study conduct will be an independent organisation, it will now be called the Independent Data Monitoring Committee (IDMC) rather than the Data Safety Monitoring Board (DSMB).

Appendix H (Meningococcal carriage and mucosal immunity to *Neisseria meningitidis* in the African meningitis belt) has been restructured and additional information on the sample size included so that it complies with PATH's guidelines for protocols.

The following items were amended on 02 October 2003:

GSK Biologicals has changed their monitoring system from CPMS to GSK's clinical trials tracking tool, eTrack, with study identification by eTrack study number and abbreviated title. Therefore, throughout the protocol, the CPMS number and alias: 759346/009 (DTPwHB/HIBMenACTT-009) has been changed to the eTrack study number and abbreviated title: 759346/009 (DTPwHB/HIBMenACTT009); eTrack has also been added to the Glossary of Terms.

Sponsor Information and/or Title pages

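### Section 10.6.2 still tabulates serology in the mother, whose blood is no longer drawn, and omits the infant pre-dose-1 time point that replaced it

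*Protocol*

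**What the plan says.** Section 10.6.2 of the Protocol lists the time points at which GMCs/GMTs and seropositivity or seroprotection rates are tabulated: "one month after the third dose of the primary vaccination course, and in the mother prior to her" child's vaccination. For the infant it gives one month after dose 3. The only pre-vaccination time point is the mother's.

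The rest of the current text has no such sample:

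- The Synopsis and section 3 list four blood samples per subject, the first "immediately before the first dose of the primary vaccination course". Section 5.4 has the infant bled at Visit 1, and section 5.5.2 places the samples at Visits 1, 4, 6 and 7.
- Section 5.5.3 states: "Pre-vaccination (Day 0) serum samples will be tested in all subjects for antibodies against SBA-MenA, SBA-MenC, anti-PSA, anti-PSC, diphtheria toxoid, pertussis antigen" and hepatitis B surface antigen. It excludes anti-tetanus and anti-PRP at Day 0 and mentions no maternal serum.
- Section 10.2 defines pre-primary secondary endpoints in the infants, including anti-BP seropositivity and concentration.

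The Amendment 2 rationale in Appendix I explains the change. The sponsor decided "to drop the planned blood sampling from the mother" and to bleed the infants instead, because "the response to the vaccine (especially to the hepatitis B, diphtheria, pertussis and meningococcal serogroups A and C antigens) can be affected by these levels".

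For the anti-BP co-primary criterion, step 6 of the inferential analysis reads: "If, in addition, the upper limit of the 95% CI for the anti-BP GMC ratio (control vaccine / new vaccine) is below 1.5", non-inferiority is concluded. No model or baseline term is stated. Section 10.5 says that missing measurements are not replaced and that subjects with missing values drop out of the analysis concerned.

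**The concern.** The analysis section asks for results on a person from whom no serum is taken, and is silent on the sample that took its place. That sample costs the infants an extra bleed at 6 to 8 weeks of age. Amendment 2 raised enrolment from 260 to 280 in case the bleed increased drop-out. An analysis that follows 10.6.2 literally would yield an empty maternal table and no infant pre-vaccination table, although 10.2 promises those endpoints.

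There is also a missed opportunity. The sponsor's own reason for the new sample is that the pre-vaccination level can affect the response, pertussis included. The anti-BP ratio is the one co-primary criterion that compares means, and a pre-dose anti-BP value is now planned for every infant. A prognostic covariate identified in advance could be used at no cost in data.

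**Working it through.** **The contradiction.** No arithmetic applies; the current sections are set side by side.

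| Section | Pre-vaccination serum |
|---|---|
| Synopsis, 3, 5.4, 5.5.2 | infant, Visit 1 |
| 5.5.3 | infant, Day 0; no anti-PRP or anti-tetanus |
| 10.2 | infant, pre-primary endpoints |
| 10.6.2 | mother |
| 10.6.1 | demographics only |
| 10.7.1 | post-dose 3, pre-booster and post-booster only |

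All of these are live text, so this is not merely a difference from the amendment log. The log shows only how it arose: for 10.6.2, Amendment 2 records a change to the first paragraph alone.

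**The anti-BP ratio: the plan's own figure.** Inputs from section 10.3 and Table 10-2: SD of log10 concentration 0.298, 110 evaluable infants per group, margin 1.5, one-sided alpha 0.025, identical GMCs.

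- Margin: log10(1.5) = 0.1761.
- Standard error: 0.298 × √(2/110) = 0.0402.
- Power: Φ(0.1761/0.0402 − 1.96) = Φ(2.42) = 99.2%. The noncentral t with 218 df also gives 99.2%. The stated 99.0% reproduces.
- Half-width of the 95% interval as a ratio factor: 10^(1.96 × 0.0402) = 1.199.

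**With baseline adjustment.** The Protocol gives no correlation r between pre-dose and post-dose-3 log10 anti-BP, so r is assumed and a range shown. The residual SD is 0.298 × √(1 − r²), and the interval on the log scale shrinks by 1 − √(1 − r²). If the groups differ at baseline by 2 standard errors, the unadjusted log10 ratio shifts by |r| × 2 × 0.0402.

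| Assumed \|r\| | Residual SD | Power | Interval narrower by | Half-width factor | Shift from 2-SE imbalance |
|---|---|---|---|---|---|
| 0.2 | 0.292 | 99.4% | 2% | 1.194 | 1.04 |
| 0.3 | 0.284 | 99.6% | 5% | 1.189 | 1.06 |
| 0.5 | 0.258 | 99.9% | 13% | 1.170 | 1.10 |

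If the 2-SE imbalance falls in the unfavourable direction, the power of the unadjusted test, conditional on that imbalance, is about 97% (|r| = 0.3) or 95% (|r| = 0.5). With a true ratio of 1, the expected upper limit is then about 1.06 × 1.199 = 1.27 or 1.10 × 1.199 = 1.32, still below 1.5.

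**The case against.** The strongest case on the other side is that this is leftover wording. With no maternal serum, no wrong number can be produced. Section 10.2 already fixes the infant thresholds, 10.6.2 already gives the estimators, and an analysis plan that is not shown may list the right time point. It stands that the consequence is limited to descriptive secondary tables, and that only the time point is missing, not a method. It does not remove the contradiction: the Protocol did not leave the time points to another document but stated them, and named the wrong person.

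On anti-BP, a reader might infer that the co-primary test is faulty, underpowered or committed to an unadjusted t-test. The documents do not support that. An unadjusted comparison is valid under 1:1 randomization. Its power is about 99%, and even a 2-SE imbalance would rarely change the conclusion. The t-test appears only in the caption of the power table; step 6 names no model, and a covariate is commonly settled in the analysis plan. The rationale in Amendment 2 says that pre-vaccination levels can affect the response, but does not promise adjustment.

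Two practical objections also stand:

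- Keeping infants without a baseline value in the model conflicts with 10.5 unless an exception is written.
- Missing values are foreseeable. The Visit 1 sample may be as small as 2.0 ml, and at Day 0 anti-BP is tested after SBA-MenA, SBA-MenC, anti-diphtheria and anti-HBs when serum is short. Pre-dose values below 15 EL.U/ml are set to half the cut-off, which may weaken the correlation.

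**Conclusion.** Section 10.6.2 contradicts the current sampling schedule, serology plan and endpoints, and should be corrected. This part rests on the text alone and needs no assumption. It affects descriptive secondary tabulations, not the validity of any co-primary conclusion.

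The anti-BP adjustment is a recommendation, not the repair of an error. The gain in power is under one percentage point, from about 99.2% to between 99.4% and 99.9% for |r| of 0.2 to 0.5. The more useful return is an interval about 5 to 13% narrower and protection against a shift of about 6 to 10% in the ratio, both for an assumed |r| of 0.3 to 0.5. If the true correlation is weaker, the benefit is smaller; the sample size is unaffected either way.

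**What to change.** 1. In the descriptive analysis of 10.6.2, replace the maternal phrase with: *in the infant just before dose 1, for the assays tested at Day 0 in section 5.5.3*. This leaves out anti-PRP and anti-tetanus, which are not tested then.
2. Optionally, define the step-6 ratio as the adjusted GMC ratio from an ANCOVA on log10 post-dose-3 anti-BP with group and log10 pre-dose anti-BP, and report the unadjusted ratio as a sensitivity analysis. Keep the margin and the order of testing as they are.
3. If item 2 is adopted, write an exception into 10.5 so that infants with a post-dose-3 result but no Day 0 anti-BP stay in the model. Use a missing-baseline indicator or the mean across both groups for the covariate only; the outcome is never imputed.

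The cost is wording in 10.6.2 and 10.5, and one covariate in one model. No new sample, assay or subject is needed.
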